3.7. Schedule of Events

The timing of all study assessments is outlined in the Schedule of Events (Table 1) below.

Table 1: Schedule of Events

Assessment	Screening Day -35 to -3 Visit 1	Baseline Day 0 Visit 2	Treatment Day 7 Visit 3	Follow-Up Day 14 Visit 4
Written Informed Consent	X		⇒	
Subject Demographics	X			
Urine Drug Screen (Instant Exam, on site)	X	X	X	X
Urine Pregnancy Test	X	X	X	X
MINI	X			
Medical and Psychiatric History	X			
Prior and Concomitant Medication Recording	X	X	Х	х
n				
LSAS	X			X

AD-ST-33.06 Effective date: 12-Nov-2020

Assessment	Screening Day -35 to -3 Visit 1	Baseline Day 0 Visit 2	Treatment Day 7 Visit 3	Follow-Up Day 14 Visit 4
Hamilton Depression Scale	X			X
C-SSRS	X	X (end of visit)c	X (end of visit)c	X
Physical Examination and Examination of Nasal Passages	X			X
Vital Signs	X	X	X	X
Electrocardiogram	X			X
Blood Tests and Urinalysis	X			X
Inclusion/Exclusion Review	X	X		
Investigational Product Administration Training	X			
SUDS Introductiona		X		
Investigational Product Administration		x	X	
Public Speaking Challenge ^b		X	X	
Randomization			X	8
PGI-C Scale				8 .
CGI-I Scale			X	
Adverse Events Recording		X	X	X

Abbreviations: C-SSRS = Columbia Suicide Severity Rating Scale; CGI-I = Clinical Global Impression of Improvement; LSAS = Liebowitz Social Anxiety Scale; MINI = Mini-International Neuropsychiatric Interview; PGI-C= Patient Global Impression of Change; SUDS = Subjective Units of Distress Scale

- Introduce the SUDS to the subject and provide scores in relation to feelings of distress (see protocol).
- b. Public Speaking Challenge involves the collection of SUDS scores from the subject and is outlined in the protocol.
- c. The C-SSRS at Visits 2 and 3 should be administered at the end of the visit, i.e., after investigational product administration and public speaking challenge.

4. Statistical Analysis and Reporting

4.1. Introduction

Data processing, tabulation of descriptive statistics, calculation of inferential statistics, and graphical representations will primarily use SAS (release 9.4 or higher). If the use of other

software is warranted, the final statistical methodology report will detail what software was used for what purposes.

Unless otherwise stated, all continuous (quantitative) variable summaries will be presented by treatment group and include the number of subjects with non-missing values (n), mean, SD, minimum, first quartile (Q1), median, third quartile (Q3), and maximum.

Unless otherwise stated, all categorical (qualitative) variable summaries will be presented by treatment group and include the frequency and percentage of subjects who are in the particular category or each possible value. In general, the denominator for the percentage calculation will be based upon the total number of subjects in the relevant study population with non-missing values.

The minimum and maximum will be reported with the same degree of precision (i.e., the same number of decimal places) as the observed data. Measures of location (mean, median, Q1, and Q3) will be reported to 1 degree of precision more than the observed data and measures of spread (SD) will be reported to 2 degrees of precision more than the observed data.

Percentages <100% will be presented to 1 decimal place and percentages of 100% will be reported with no decimal place. Counts of zero will be presented without percentages.

Unless otherwise indicated, all statistical tests will be conducted at the 0.05 significance level using 2-tailed tests, and *P* values will be reported. Corresponding 95% confidence intervals (CIs) will be presented for statistical tests.

To control for the overall type I error rate, a fixed-sequence testing strategy will be used. If statistical significance is declared for the primary endpoint, formal hypothesis testing will be done for the secondary endpoint. If a non-significant *P* value is reached for the primary endpoint, *P* values for the secondary endpoint will be considered exploratory. The *P* values from the exploratory endpoints are not included in the fixed-sequence testing strategy and are included for informational purposes only. The planned sequence of hypothesis testing is detailed in Section 6.1.3.

4.2. Interim Analysis and Data Monitoring

No interim analysis is planned.

5. Analysis Populations

The following analysis populations are planned for this study:

All Subjects Population: All subjects who sign an informed consent, participate in a
Screening visit, and are entered into the eCRF will be included in the All Subjects
population. The All Subjects population will be used for summaries of subject disposition
and protocol deviations.

- **Safety Population:** All subjects who receive IP will be included in the Safety Population. For analysis of the Safety Population, each subject will be analyzed by the actual treatment received, even if it differs from the subject's randomized treatment assignment. Adverse events (AEs) will be classified by time of occurrence and Visit 3 (Treatment) group assignment to more clearly identify those arising after exposure to and those arising after exposure to The Safety Population will be used for safety analyses.
- **Intent-to-Treat (ITT) Population:** The ITT Population in the study includes all subjects who are randomized. For analyses of the ITT Population, each subject will be analyzed by their randomized treatment assignment, even if the subject did not receive the assigned treatment or did not follow the protocol until completion. The ITT Population will be used for efficacy analyses.
- Per Protocol (PP) Population: The Per Protocol (PP) Population includes all subjects who have non-missing average SUDS scores during the 5-minute public speaking challenges at Visit 2 (Baseline) and Visit 3 (Treatment) and no important protocol deviations that would have an impact on statistical analysis. For analyses of the PP Population, each subject will be analyzed by the actual treatment received, even if it differs from the subject's randomized treatment assignment. The PP Population will be used for a sensitivity analysis of the primary efficacy endpoint (Section 8.1.2).

Inclusion in the analysis populations will be determined prior to database lock. Assignment of subjects to populations will be confirmed at a blinded data review meeting to be held before the study database is locked.

6. **General Issues for Statistical Analysis**

6.1. **Statistical Definitions and Algorithms**

6.1.1. Baseline

Baseline for each study assessment is defined in Table 2.

Table 2: Baseline Definitions

Parameter	Baseline
Safety Variables (clinical laboratory assessments, vital signs, ECGs, physical examinations)	The last non-missing assessment before the first dose of study drug given at Visit 2 (Baseline).
C-SSRS Scores	Scores on the Baseline version of the C-SSRS given at Visit 1 (Screening).

divided by the number of SUDS scores recorded during the speech performance.

Average Anticipatory SUDS Score

Sum of Visit 2 (Baseline) SUDS scores

divided by the number of recorded SUDS scores.

LSAS total score, HAM-D total score.

Total score at Visit 1 (Screening).

Abbreviations: CGI-I = Clinical Global Impression of Improvement; ECG = electrocardiogram; C-SSRS = Columbia-Suicide Severity Rating Scale; Scale; LSAS = Liebowitz Social Anxiety Scale; PGI-C= Patient Global Impression of Change; SUDS = Subjective Units of Distress Scale

6.1.2. Adjustments for Covariates

Planned analysis of covariance (ANCOVA) analyses will adjust for analysis site (Section 6.1.6) and the baseline of the target endpoint by including them as terms in the model. The comparison of binomial proportions for the secondary endpoint will be presented overall and by strata.

6.1.3. Multiple Comparisons

[figure not shown]
The type I error rate of $\alpha = 0.05$ will be maintained for the study by using a fixed-sequence testing strategy for the primary and secondary endpoints. Testing of the secondary endpoint will proceed only if the primary endpoint achieves statistical significance. No multiple comparisons adjustments will be made for the exploratory endpoints as the analyses are included for descriptive purposes only. All P values for each comparison will be provided in the summary tables for informational purposes.

The testing will be done in the following order:

1. Primary efficacy endpoint: difference in average SUDS score during the Visit 3 (Treatment) public speaking challenge versus the average SUDS score during the

AD-ST-33.06 Effective date: 12-Nov-2020

Version Final 1.0 | Date 28-Jun-2022 | AD-ST-33.06 Effective date: 12-Nov-2020 | Page 21 of 140

6.1.4. Handling of Dropouts or Missing Data

Data will be included in the analysis according to the analysis visit windows described in Section 6.1.5.

It is expected that all study subjects who are randomized at Visit 3 (Treatment) will complete the Visit 3 (Treatment) public speaking challenge immediately after randomization and be included in the primary efficacy analysis. If a subject has incomplete scores during the 5-minute interval, then their average SUDS score will be calculated using the non-missing scores. If all public speaking challenge Visit 3 (Treatment) SUDS scores are missing for unanticipated reasons (intercurrent events) that arise during Visit 3 (Treatment), the average SUDS score will be set to missing. If the fraction of missing change from baseline to Visit 3 (Treatment) average SUDS scores in the ITT population is greater than 0.05, multiple imputation of the change from baseline to Visit 3 (Treatment) average SUDS scores will be carried out for the primary efficacy analysis. The fraction of missing average change from baseline in average SUDS scores will be computed as described in Section 6.1.7.2.

only change from baseline SUDS scores will be imputed. Other efficacy and safety data will not be imputed and will be analyzed as observed.

The imputation approach has 2 broad components: i) the multiple imputation process for the placebo and PH94B data; and ii) the analysis method that will be used to draw inference regarding the primary causal estimand, along with the method for combining the results across the multiply-imputed datasets. The primary causal estimand is defined in Section 8.1.

The imputation approach for the primary efficacy endpoint will be carried out in SAS using the fully conditional specification (FCS) method with a regression model (Carpenter and Kenward, 2013). The method assumes data are missing at random (MAR). Thus, subjects with missing values will have imputed values similar to other subjects with comparable observed profiles in the regression variables. The imputation will be carried out separately within each treatment group. The regression model will include the following variables: baseline SUDS score, sex, age, baseline LSAS total score, and analysis site. For each imputation process, a total of 25 complete datasets will be created. The random seeds to be used in the imputation steps are 157340717 and 127581968 for the PH94B and placebo arms, respectively.

The analysis for the multiple imputation will match that described for the primary efficacy analysis (Section 8.1.1). Results from the multiply-imputed datasets will be combined using the standard Rubin's rules for multiple imputation (Little and Rubin, 1987) and will be done in SAS using PROC MIANALYZE.

Analysis visits will be assigned based on the nominal visit recorded in the study database.

6.1.6. Pooling of Sites

Analysis sites (pooled sites) will be created if sites have fewer than 6 randomized subjects. Sites will be ordered by the number of randomized subjects. The smallest study site will be combined with the next smallest study site. These 2 sites may be combined with the next smallest study site if the combined number of subjects remains less than 6. This process will be continued until this first pooled site has 6 or more randomized subjects. Once pooling is completed for the first pooled site, the pooled site and all unpooled sites will be reordered by the number of randomized subjects. If the new smallest site has fewer than 6 randomized subjects, the pooling will proceed again as described above to create a second pooled site, followed by reordering of pooled and unpooled sites by the number of randomized subjects. The process will repeat until the smallest site has 6 or more randomized subjects. If, in combining the 2 smallest sites, the resulting new analysis site becomes the largest study site (i.e., more subjects than present in the initial largest site), the combining of sites will be halted and not performed. The final determination of pooled sites will be made prior to database lock.

6.1.7. Definitions and Derived Variables

6.1.7.1. General

- Age = Integer difference in years between the subject's date of informed consent and date
 of birth.
- Change from Baseline to Visit X in Parameter Y = Value at Visit X minus the value at Baseline (as defined in Table 2).
- Treatment Duration = Treatment end date minus treatment start date plus 1.
- Height (cm) and Weight (kg) = Height (cm) will be calculated as height (in) times 2.54. Weight (kg) will be calculated as weight (lb) times 0.4536.
- Percent Change from Baseline to Visit X in Parameter Y = Change from Baseline to
 Visit X in Parameter Y divided by the value at Baseline (as defined in Table 2) multiplied
 by 100.
- Shift from Baseline to Visit X in Parameter Y Categories = Cross-tabulation of below
 the lower limit of the normal range, within the limits of the normal range, and above the
 upper limit of the normal range at Baseline (as defined in Table 2) versus at Visit X.
- Study Day = Event date minus date of the first dose of study drug plus 1 for events occurring on or after the first dose. Event date minus the date of the first dose of study drug for events occurring before the first dose.

Temperature (C°) = Temperature (F°) times 5 divided by 9.

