 - a. Obtain urine sample for urine drug screen: Instant Exam to be performed on site, with results thoroughly documented in the source; urine sample to be sent to central laboratory for confirmation if on-site screen is positive
 - b. For females of child-bearing potential, obtain urine sample and complete on-site urine pregnancy test
- Medical and psychiatric history and diagnosis (usually starting with MINI) to include:
 - a. Administer MINI (7.0.2)
 - b. Obtain medical history (including nicotine, alcohol use, and menstrual information on women of childbearing potential) and psychiatric history
 - Record prior and concomitant treatment and medication use (medication name, dose, and frequency)

Amendment 3, Version 4.0

- 1.0
- 4. Standardized assessments (usually starting with LSAS but per investigator judgement based on the MINI) to include:
 - a. Administer LSAS

AD-MW-07.08 18-Jun-2019 Page 41 of 101

- b. Administer HAM-D
- c.
- d. Administer C-SSRS (Long Term/Recent)
- 5. Physical assessments (recommend blood draw last to avoid any potential impact on vitals and ECG assessment) to include:
 - a. Perform physical examination, including height (inches), body weight (pounds), body temperature (°F), and vital signs after the subject has rested for 5 minutes: seated systolic and diastolic blood pressure, heart rate, and respiratory rate. The physical examination includes a review of the nasal passages
 - b. Obtain 12-lead ECG in supine position after the subject has rested for 5 minutes
 - c. Obtain blood and urine samples for evaluation by the central clinical laboratory, including hematology, chemistry, thyroid functioning, and urinalysis (refer to Section 10.3.2.1.1 for complete list)
- 6. After these assessments are complete, review all inclusion and exclusion criteria
- 7. Train subjects on the use of IP and dosing. The subject will be given instructions on:
 - a. how to position the nozzle in the nasal passages and self-administer IP, using a demonstration vial
 - b. number of sprays per nostril per dose (one per nostril)

Procedures for rescreening subjects who initially fail to meet study entry criteria are described in Section 14.3.

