10.2.4 Follow-up (or Early Termination) Evaluation

At Visit 4, 1 week (± 2 days) after Visit 3, the following procedures will be performed:

- Obtain 12-lead ECG in supine position after the subject has rested for 5 minutes
- Obtain blood and urine samples for evaluation by the central clinical laboratory, including hematology, chemistry, thyroid functioning, and urinalysis (refer to Section 10.3.2.1.1 for complete list)

Amendment 3, Version 4.0

AD-MW-07.08 18-Jun-2019 Page 46 of 101

- Perform physical examination, including height (inches) and body weight (pounds). The physical examination also includes an examination of the nasal passages
- Measure vital signs after the subject has rested for 5 minutes: seated systolic and diastolic blood pressure, heart rate, respiratory rate, and body temperature (°F)
- Obtain urine sample for urine drug screen: Instant Exam to be performed on site, with results thoroughly documented in the source; urine sample to be sent to central laboratory for confirmation if on-site screen is positive
- For females of child-bearing potential, obtain urine sample and complete on-site urine pregnancy test
- •
- Administer HAM-D
- •
- Administer C-SSRS (Since Last Visit)
- Record concomitant medication use
- Review and record AEs

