9.3. Vital Signs

Descriptive summaries of observed values and changes from baseline will be calculated for systolic blood pressure (mmHg), diastolic blood pressure (mmHg), heart rate (beats/min), respiratory rate (breaths/min), and temperature (°C) by treatment group, subjects not randomized and overall subjects and by study visit.

The number of subjects with vital signs values categorized as below, within, or above normal ranges will be tabulated showing change from baseline (shift tables) for each parameter by visit by treatment group and overall.

9.4. 12-Lead Electrocardiograms

The number and percentage of subjects with normal and abnormal 12-lead ECG findings will be summarized for each treatment group, subjects not randomized and overall subjects at each study visit. Abnormal results will be grouped as clinically significant and not clinically significant.

Descriptive summaries for the observed results and change from baseline will be presented for 12-lead ECG measures of PR interval (msec), QRS interval (msec), and heart rate for each treatment group and overall subjects at each study visit. If triplicate reads are taken, the mean of the reads will serve as the observed value at the specific visit.

A comparison of QT and QTcF results will be presented. Summary statistics for baseline values at Visit 1 (Screening) and Visit 4 (Follow-Up) will be displayed by treatment group and overall subjects for QT interval (msec) and QT interval corrected for heart rate using Fridericia's formula (QTcF) (msec). In addition, the number and percent of subjects in each treatment group who experienced a change >30 msec or a change >60 msec will be presented.

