Table 14.3.5.3.3	Safety	Quantitative and Qualitative Urinalysis: Shifts from Baseline Relative to the Normal Range	
14.3.6 Other Safe	ety Data Summary	Tables	
Table 14.3.6.1.1	Safety	Vital Signs: Observed Results and Change from Baseline by Study Visit	

Table Number	Population	Table Title / Summary	
Table 14.3.6.1.2	Safety	Vital Signs: Shifts from Baseline Relative to Normal Range by Stud Visit	
Table 14.3.6.2.1	Safety	12-Lead Electrocardiogram: Observed Results and Change from Baseline by Study Visit	
Table 14.3.6.2.2	Safety	12-Lead Electrocardiogram: Summary of 12-Lead Electrocardiogram Interpretation by Study Visit	
Table 14.3.6.2.3	Safety	12-Lead Electrocardiogram: Summary of QT and QTcF Results by Study Visit	
Table 14.3.6.3	Safety	Summary of Physical Examination by Study Visit	
Table 14.3.6.4	Safety	Summary of Concomitant Medications by ATC Class and Preferred Term	
Table 14.3.6.5	Safety	Summary of Columbia Suicide Severity Rating Scale (C-SSRS) by Study Visit	
Table 14.3.6.6	Safety	Hamilton Depression Scale (HAM-D): Observed Results and Change from Baseline by Study Visit	

Table 6: Other Data Summary Tables

Table Number Population		Table Title / Summary	
14.5 Other Data	Summary Tables		
Table 14.5.1	able 14.5.1 Safety Summary of Drug Prediction Questionnaire (DPQ)		

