13.5. Planned Listing Descriptions

The following are planned data and subject data listings for protocol number PH94B-CL032.

In general, 1 listing will be produced per eCRF domain. All listings will be sorted by treatment, site, and subject number. All calculated variables will be included in the listings.

In all listings a blank line will be placed between each subject. Within a data listing, if an item appears line after line (e.g., repetition of subject number), then only the first occurrence will be displayed. Screen failures will only be presented in Listings 16.2.1.1, 16.2.2.1, and 16.2.2.3; otherwise, only enrolled subjects will be listed.

In data listings, the information for 1 subject will be kept on 1 page, if at all possible, rather than splitting a subject's information across pages.

Table 7: Planned Listings

Listing Number	Population	Listing Title / Summary
16.2 Subject Data Lis	tings	
16.2.1 Subject Discon	tinuations/Completions	
Listing 16.2.1.1	All Subjects	Subject Disposition
16.2.2 Protocol Devia	tions	
Listing 16.2.2.1	All Subjects	Inclusion and Exclusion Criteria
Listing 16.2.2.2	All Enrolled Subjects	Protocol Deviations
Listing 16.2.2.3	Screen Failures	Reasons for Screen Failures
16.2.3 Patients/Subject	cts Excluded from the Effic	cacy Analyses
Table 16.2.3.1	All Subjects	Analysis Populations
16.2.4 Demographic I	Data and Other Baseline Cl	haracteristics
Listing 16.2.4.1	All Subjects	Subject Consent and Demographics
Listing 16.2.4.2	All Subjects	Medical and Psychiatric History
Listing 16.2.4.3	All Subjects	Mini-International Neuropsychiatric Interview (MINI)
Listing 16.2.4.4	All Subjects	

Listing Number	Population	Listing Title / Summary
16.2 Subject Data Lis	tings	
16.2.5 Compliance an	d/or Drug Concentration	Data
Listing 16.2.5.1	All Subjects	Study Drug Dispensation
Listing 16.2.5.2	All Subjects	Study Drug Administration
16.2.6 Individual Effi	cacy Response Data	•
Listing 16.2.6.1	All Subjects	Subjective Units of Distress Scale (SUDS)
Listing 16.2.6.2	All Subjects	Clinical Global Impression – Improvement scale (CGI-I)
Listing 16.2.6.3	All Subjects	Patient Global Impression of Change (PGI-C)
Listing 16.2.6.4	All Subjects	Liebowitz Social Anxiety Scale (LSAS)
Listing 16.2.6.5	All Subjects	
16.2.7 Adverse Event	Listings (by Subject)	
Listing 16.2.7.1	All Subjects	Adverse Events
16.2.8 Laboratory Va	lues (by Subject)	
Listing 16.2.8.1	All Subjects	Hematology Laboratory Evaluations

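### The SAP's Fahrenheit-to-Celsius formula omits the subtraction of 32, so as written every converted body temperature is 17.78 °C too high

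*SAP*

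**What the plan says.** Among the general derived variables, SAP section 6.1.7.1 defines "Temperature (C°) = Temperature (F°) times 5 divided by 9". It is the only Fahrenheit-to-Celsius rule in either document, and nothing elsewhere corrects it.

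The input is in Fahrenheit. Protocol section 10.2.1.1 (Screening) specifies an examination "including height (inches), body weight (pounds), body temperature (°F), and vital signs", and section 10.2.4 (Follow-up) prints the same temperature unit. Sections 10.2.2 and 10.2.3, for Visits 2 and 3, require temperature to be measured but print no unit.

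The output is in Celsius. SAP section 9.3 plans summaries of observed values and changes that include "respiratory rate (breaths/min), and temperature (°C) by treatment group". It also plans counts below, within and above the normal range, "tabulated showing change from baseline (shift tables) for each parameter by visit by treatment group and overall". SAP section 13.3 lists the corresponding output as Table 14.3.6.1.1, "Vital Signs: Observed Results and Change from Baseline by Study Visit", and Table 14.3.6.1.2 for the shifts. Section 13.5 adds: "All calculated variables will be included in the listings".

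**The concern.** The two scales have different zero points, so a conversion between them needs an offset as well as a scale factor. The SAP has the factor and not the offset. A quick check shows this: 32 °F is 0 °C, but the SAP rule turns it into 17.78 °C.

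The rule is a live derivation. It stands between a variable collected in °F and tables specified in °C. If it is followed literally, the mean, median, quartiles, minimum and maximum of observed temperature are all wrong in a safety table, and so are the individual values in the listing. If the shift table also uses converted values with a Celsius range, every subject falls in the same category and the table cannot show a fever.

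**Working it through.** **Inputs**

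- Conversion as written (SAP 6.1.7.1): C = F × 5/9.
- Correct conversion: C = (F − 32) × 5/9.
- Unit collected: °F (protocol 10.2.1.1 and 10.2.4).
- Unit reported: °C (SAP 9.3).
- Change from baseline: visit value minus baseline value (SAP 6.1.7.1).

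The SAP gives no worked temperature, so there is no printed figure to reproduce.

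**Step 1. Size of the error**

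F × 5/9 − (F − 32) × 5/9 = 32 × 5/9 = 17.78 °C, whatever the reading.

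**Step 2. Values across the plausible range**

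| Reading (°F) | SAP rule, F × 5/9 | Correct, (F − 32) × 5/9 | Difference |
|---|---|---|---|
| 95.0 | 52.78 | 35.00 | 17.78 |
| 97.0 | 53.89 | 36.11 | 17.78 |
| 98.6 | 54.78 | 37.00 | 17.78 |
| 99.5 | 55.28 | 37.50 | 17.78 |
| 100.4 | 55.78 | 38.00 | 17.78 |
| 104.0 | 57.78 | 40.00 | 17.78 |

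**Step 3. Changes and spread**

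Correct change: (F₂ − 32) × 5/9 − (F₁ − 32) × 5/9 = (F₂ − F₁) × 5/9. The SAP rule gives the same expression. A rise of 1 °F is 0.556 °C under both. A constant offset also leaves standard deviations and differences between arms unchanged. This assumes °F at every visit. That matters because the SAP takes the vital-sign baseline as the last value before the Visit 2 dose. It will usually be the Visit 2 reading, for which no unit is printed.

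**Step 4. Shift table**

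The text gives no normal range for temperature. Assume an upper limit between 37.0 and 38.0 °C, applied to the converted values. The reading that the SAP rule turns into the limit is then:

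- 37.0 × 9/5 = 66.6 °F
- 38.0 × 9/5 = 68.4 °F

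Anything above 66.6 to 68.4 °F would count as above normal. Every plausible body temperature exceeds that, so all subjects land in the single cell for above normal at both baseline and follow-up. If the categories are instead formed on the °F values against a °F range, the shift table is correct.

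**Step 5. Neighbouring conversions**

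Height (inches × 2.54) and weight (pounds × 0.4536) in the same list are right. Neither needs an offset, so the error is confined to temperature.

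**The case against.** Four points can be made for the plan.

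1. **The text may have been damaged in extraction.** The temperature line has lost its bullet, and the SUDS definitions just after it have words missing without a redaction mark. But those losses leave broken sentences, whereas the temperature line is complete and ends with a full stop. There is also no evident reason to black out a unit conversion. This leaves only a small doubt.

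2. **The slip is easy to notice.** A mean body temperature near 55 °C would stand out, and a programmer would probably correct it. That lowers the chance of harm but does not make the specification right. Anyone programming strictly to the SAP would either repeat the error or depart from an approved document.

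3. **Little that matters is affected.** Changes, standard deviations and differences between arms survive, and the planned vital-sign table has no percent-change column. SAP section 9 plans no formal safety tests, and protocol section 13.1.5.3 does not name temperature among the vital signs to be summarized. All of this stands, and it is why the point is minor.

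4. **The shift-table harm is conditional.** It needs a Celsius range applied to converted values. That is correct. The text available gives no numeric range for any vital sign, and the SAP footers count 140 pages, so a range may be stated on pages not seen here. The certain consequence of following the line is limited to the observed values in Table 14.3.6.1.1 and the listing.

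**Conclusion.** The concern holds. The formula in SAP section 6.1.7.1 is wrong as written, by a constant 17.78 °C. Observed Celsius temperatures in the summary table and the listing would be wrong if it is programmed literally. The shift table would also be uninformative if it uses converted values with a Celsius range.

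The conclusion about observed values needs only that the line is followed and that the readings are in °F, which the formula itself presumes. The conclusion that changes from baseline are unaffected also needs °F at Visits 2 and 3. Severity is minor: the effect is confined to descriptive safety reporting and does not touch efficacy, sample size or type I error.

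**What to change.** Replace the line in SAP section 6.1.7.1 with: Temperature (°C) = (Temperature (°F) − 32) × 5/9.

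This costs one line of SAP text and one line of code. It needs no new data and changes no efficacy result. When the code is corrected, it is worth confirming that the shift categories use the same unit as the normal range applied to them; this is a programming check and needs no further SAP change.

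The SAP was written to protocol version 3.0 and states that no interim analysis is planned, while protocol version 4.0 adds one. If the SAP is revised for that reason, this correction can go into the same revision.
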